#### **6.3 Subject Withdrawals**

The participants may leave the study at their own discretion, or the experts from the gastrointestinal or anorectal department in each site may determine that it is the best for the subject to discontinue participation (due to worsening of symptoms, or the occurrence of a serious adverse event).

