### 9. Sample Size Calculation

The primary outcome is the proportion of participants with 3 or more mean weekly CSBMs over weeks 3-8. According to our previous 60-size pilot study, the proportion was 31.67% by EA; and the proportion by prucalopride was 30.9% 6. The non-inferiority sample size calculation formula is listed as below:

$$\begin{split} n &= \frac{(Z_{1-\alpha} + Z_{1-\beta})^2 [p_1(1-p_1) + p_2(1-p_2)]}{(\epsilon - \delta)^2} \\ &= \frac{(1.645 + 0.845)^2 [0.3167 \times (1 - 0.3167) + 0.309 \times (1 - 0.309)]}{[0.3167 - 0.309 - (-0.1)]^2} = 230 \end{split}$$

To assess the non-inferiority between the treatment and control groups, a sample size of 276 for each group will be sufficient, with a non-inferior margin of -10%, one-sided 5% level of significance, a power of 80% and allowing for a 20% dropout. In this trial, we aim to recruit 560 participants considering the balance of 14 centers, with 40 participants of each center.

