# 13.2 Statistical Analysis Set

Modified intention-to-treat (mITT) set will be defined as all the participants who accept randomization with baseline data. Per-protocol (PP) set will be composed of all randomly assigned participants without major protocol violations, which defined as the participants in EA group who were unable to complete 23 or more of the EA sessions, or the participants in control group who take prucalopride less than 180 days; or the participants who use prohibited medications and others which will be deemed to affect the interpretation of the primary outcome.

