### 13.3 General Principles of Statistical Analysis

The primary outcome was one-tailed test at significance levels of 0.025. All the other statistical analyses were two-tailed tests, at a significant level of 0.05, using SAS software, version 9.4 (SAS Institute Inc, Cary, North Carolina, USA). For measurement data, mean±standard deviations (M±SD), median, minimum, maximum, were presented. Differences between groups were compared using group t tests or nonparametric tests. Comparisons with the baseline used paired t tests or nonparametric tests. For counting data, cases and percentages were presented, and differences between groups were compared using Chi-squared tests, Fisher's exact probabilities or non-parameters tests. For abnormal distributed data, differences between groups were compared using nonparametric tests. Missing data for the primary outcome were imputed using the multiple imputation (MI) method under the missing at random assumption for the mITT population. The results for the PP set were used as the sensitivity analysis for the multiple imputation. For secondary outcomes, no imputation was used and observed data were used for analyzing.

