#### 13.6 Secondary Outcomes

- (1) For the proportion of participants with 3 or more mean weekly CSBMs, the Cochran-Mantel-Haenszel (CMH) test, stratified by center, was used to test a hierarchical comparison between two groups. Assessing timeframe: weeks 1-2, 11-12, 15-16, 19-20, 31-32.
- (2) For the proportion of participants with ≥1 increase of mean weekly CSBMs from baseline, the Cochran-Mantel-Haenszel (CMH) test, stratified by center, was used to test a hierarchical comparison between two groups. Assessing timeframe, weeks 1-2, 3-8, 11-12, 15-16, 19-20, 31-32.
- (3) For the change from baseline in mean weekly CSBMs, a repeated measures analysis of variance was used, setting group, time, and the interaction of group and time as the fixed effects; besides, the baseline CSBMs data and usage of rescue medicine were set as the covariate. Assessing timeframe: weeks 1-2, 3-8, 11-12, 15-16, 19-20, 31-32.
- (4) For the change from baseline in mean weekly SBMs, the same statistical analysis was conducted in accordance with the change from baseline in mean weekly CSBMs. Assessing timeframe: weeks 1-2, 3-8, 11-12, 15-16, 19-20, 31-32.
- (5) For the mean scores of straining, the Wilcoxon rank-sum test was used. Assessing timeframe: weeks 1-2, 3-8, 11-12, 15-16, 19-20, 31-32.
- (6) For the mean scores of stool consistency, the Wilcoxon rank-sum test was used. Assessing timeframe: weeks 1-2, 3-8.
- (7) For the time to the first CSBM (counting by days), the Wilcoxon rank-sum test was used.
- (8) For the change in mean scores of PAC-QOL between two groups, t test was used. Assessing time point: week 4 and week 8.
- (9) Rescue medicine usage: For the proportion of participants using rescue medicine (bisacodyl or glycerine enema), the Chi-square test was used. For the average dosage of bisacodyl or glycerine enema used per week, the Wilcoxon rank-sum test was used. Assessing timeframe: weeks 1-2, 3-8, 11-12, 15-16, 19-20, 31-32.

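### The per-protocol analysis cannot test the missing-at-random assumption behind the primary multiple imputation, and the follow-up responder rates rest on observed cases only

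*Supplement*

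**What the plan says.** SAP 13.3 sets three rules.

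- Primary outcome: "Missing data for the primary outcome were imputed using the multiple imputation (MI) method under the missing at random assumption for the mITT population".
- Check on that imputation: "The results for the PP set were used as the sensitivity analysis for the multiple imputation".
- Everything else: "For secondary outcomes, no imputation was used and observed data were used for analyzing".

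The imputation model, its auxiliary variables and the number of imputations are not given. SAP 13.5 to 13.7 add no analysis that varies the assumption about missing outcomes, and section 7.3 of the final protocol has no missing-data rule.

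Under SAP 13.2 the PP set leaves out "the participants in EA group who were unable to complete 23 or more of the EA sessions", "the participants in control group who take prucalopride less than 180 days", and users of prohibited medication.

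For the secondary responder rate, SAP 13.6 says: "For the proportion of participants with 3 or more mean weekly CSBMs, the Cochran-Mantel-Haenszel (CMH) test, stratified by center, was used". Its windows are weeks 1-2, 11-12, 15-16, 19-20 and 31-32. The sample size in SAP 9 is built on "a power of 80% and allowing for a 20% dropout".

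**The concern.** A sensitivity analysis for MI should ask how far the result moves if the missing outcomes are worse than MAR implies. PP asks a different question: what the result is among people who took enough treatment. If the two agree, nothing has been learned about the participants whose weeks 3-8 data are missing.

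Dropout related to outcome is plausible here. Participants are not among those blinded (SAP 5), they record their own bowel movements (SAP 10.1), and SAP 6.3 names worsening symptoms as one ground for discontinuation. A non-inferiority claim could then depend on imputed responses that no planned analysis examines.

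SAP 1 also asks whether the effect of EA lasts 3 or 6 months. The responder rates that bear on this would describe only those who still return diaries.

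**Working it through.** **1. Inputs.** From SAP 9: responder rates of 31.67% (EA) and 30.9% (prucalopride), a 20% dropout allowance, and 560 participants, so 280 per arm at 1:1. From SAP 13.1: a margin of -10 points. From SAP 13.3: one-sided alpha of 0.025. The split of dropout by arm and the response rate among dropouts are not in the documents. They are assumptions, and I vary them.

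**2. The plan's own figure.** (1.645 + 0.845)² × [0.3167 × 0.6833 + 0.309 × 0.691] / 0.1077² = 229.8, so 230 per group. The plan's 276 is 230 × 1.2.

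**3. What PP removes.** The EA rule is 23 of 28 sessions (82%), all within weeks 1-8. The prucalopride rule is 180 of 32 × 7 = 224 days (80%), reached at 180/7 = 25.7 weeks. The primary window closes at day 56. Someone who stops prucalopride at week 8 can have complete primary data and still leave the PP set. PP therefore discards observed primary outcomes in one arm under a rule that reaches far beyond the window, and it makes no statement about missing ones.

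**4. Observed-case responder rates.** If p is the true rate among all randomised, d the missing fraction, and every missing participant is a non-responder, the observed rate is p/(1 - d).

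- Prucalopride: 0.309/0.80 = 38.6%; with 10% missing, 0.309/0.90 = 34.3%.
- EA: 0.3167/0.80 = 39.6%; with 10% missing, 35.2%.

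These are the weeks 3-8 planning rates, used to illustrate the follow-up windows.

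**5. Primary difference at the margin.** Take EA 20.9% and prucalopride 30.9%, a true difference of -10 points, with all dropouts non-responders. In large samples, MAR imputation by arm without informative auxiliary data gives the same p/(1 - d). With n = 280 × (1 - d) per arm and the unpooled normal approximation:

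P(false non-inferiority) = 1 - Φ(1.96 - (apparent difference + 0.10)/SE).

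| Dropout EA/prucalopride | Apparent rates | Apparent difference | False non-inferiority |
|---|---|---|---|
| 0%/0% | 20.9% / 30.9% | -10.0 | 2.5% |
| 10%/20% | 23.2% / 38.6% | -15.4 | 0.06% |
| 20%/20% | 26.1% / 38.6% | -12.5 | 0.6% |
| 20%/10% | 26.1% / 34.3% | -8.2 | 6.3% |
| 30%/10% | 29.9% / 34.3% | -4.5 | 23.8% |

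For 20%/10%: SE = √(0.2612 × 0.7388/224 + 0.3433 × 0.6567/252) = 0.0419; (-0.0821 + 0.10)/0.0419 = 0.43; 1 - Φ(1.96 - 0.43) = 6.3%.

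**6. Less extreme dropouts.** At 25%/15% dropout and a true -10 points, let dropouts respond at 0, 25, 50, 75 or 100% of the completers' rate. The apparent difference is then -8.5, -9.1, -9.5, -9.8 or -10.0 points.

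**7. Missing = non-responder as the check.** If MAR holds and both arms lose 20%, each rate is multiplied by 0.8: 16.7% against 24.7%, a difference of -8.0 points. With 280 per arm, SE = √((0.1672 × 0.8328 + 0.2472 × 0.7528)/280) = 0.0341, and false non-inferiority is 1 - Φ(1.96 - 0.02/0.0341) = 8.5%. This rule can itself favour non-inferiority.

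**The case against.** MI on the mITT set is a recognised primary analysis, and a PP analysis commonly accompanies a non-inferiority trial. That stands: the fault lies in naming PP as the check on MI, not in reporting it.

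The plan also works to limit missing data. Sections 2.4.7.4 and 5.3 of the final protocol ask for continued follow-up of non-adherent participants by phone, message or visit. The 20% is a sample-size allowance not tied to week 8, so missingness in the primary window may be lower. This also stands, but it reduces the amount of missing data and does not test the assumption for what remains.

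MAR imputation that uses diary weeks before dropout would impute low response for those already doing badly. That is right, and diaries are daily through week 8. A reader might infer that MI simply copies the completers' rate to dropouts; the documents do not establish this, because the model is unspecified. The results in step 5 are for a model without such information.

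A reader might also infer that PP exclusions are largely the people with missing data. The 180-day rule and the continued follow-up both speak against assuming so.

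Finally, the repeated-measures models for CSBM and SBM change in SAP 13.6 could use partial data validly under MAR if fitted by likelihood, which is not stated. The observed-case point is therefore confined to the responder rates.

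**Conclusion.** The concern holds in a bounded form. The one analysis named as a check on MAR cannot check it, and the follow-up responder rates are observed-case rates with no alternative beside them. Both rest on the text alone.

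The size and direction of bias in the primary difference rest on assumptions. Equal loss of non-responders makes the test conservative (0.6% at 20%/20%). It becomes anti-conservative only if EA loses more such participants (6.3% at 20%/10%, 23.8% at 30%/10%), and nothing in the documents predicts that split.

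A reader might infer that MI could flatter EA by 0.20 × 31.67% = 6.3 points, or 63% of the margin. That requires every EA dropout to be a non-responder and no matching loss under prucalopride, whereas SAP 9 applies one 20% allowance to both groups. Nor do the documents show that people leave mainly for lack of efficacy: SAP 6.3 also lists serious adverse events and the participant's own choice. Because the split is unknown in advance, the check should be pre-specified. This is a change that should be made; it does not invalidate the primary analysis.

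**What to change.** In SAP 13.3:

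1. Keep MI under MAR as the primary analysis. Specify the imputation model, including arm, center and the weekly diary CSBM data recorded before dropout, and state the number of imputations.
2. Replace PP as its sensitivity analysis by an arm-specific delta-adjusted MI. Lower the imputed response of EA dropouts stepwise until the lower confidence limit for the difference crosses -10 points. Report that tipping point and whether it is plausible.
3. Report PP separately, labelled as a per-protocol analysis.
4. If missing = non-responder is shown, make it a supplement only and say that it shrinks differences toward zero and can favour non-inferiority.
5. For the CSBM responder rates at weeks 11-12 to 31-32, add a supportive MI or non-responder analysis beside the observed-case result, with the number missing by arm and window.

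The cost is SAP wording, modest programming and a few more tables. No new data are needed.

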### 13.4 Participants Distribution and Demographic Data

The distribution of participants among centers after randomization and the demographic data and outcome values at baseline were described.

#### 13.5 Primary Outcome

The primary outcome was the proportion of participants with 3 or more mean weekly CSBMs over weeks 3-8. The Cochran-Mantel-Haenszel (CMH) test, stratified by center, was used to test a hierarchical comparison between two groups.

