#### 7.3 Statistical Methods

The data from the 14 centers will be pooled, and the Institute of Basic Research in Clinical Medicine, China Academy of Chinese Medical Sciences in Beijing will conduct the statistical analysis using the SAS 9.4 (SAS Institute, Cary, NC, US) software. All statistical analyses will be two-sided tests except for the primary outcome (one-sided). The level of significance will be established at 0.05. Continuous data will be represented by the mean (standard deviation), mean [95% confidence interval (CI)], or median (interquartile range); categorical data will be represented by percentages. To compare two independent samples, a t-test or nonparametric test will be used for continuous data, and a chi-square test/the Fisher exact test/non-parametric tests will be used for categorical data. For the primary outcome, the CMH test will be used to avoid the center effect.

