#### **6.1 Inclusion Criteria**

- 1) Primary chronic constipation meeting the Rome III criteria with  $\leq$ 2 mean weekly CSBMs (CSBM refers to the bowel movement without the help of drug or hands within the past 24 hours with the feeling of complete evacuation. The bowel movement beyond 24 hours after the use of medicine/hands also could be considered an SBM) in the past three months. They should conform to at least one of the following items at the same time: a) a feeling of straining during evacuation (at least once per 4 bowel movements); b) lumpy or hard stools (at least once per 4 bowel movements); c) a feeling of incomplete evacuation after a bowel movement (at least once per 4 bowel movements); e) needing the help of hands for evacuation (at least once per 4 bowel movements).
- 2) Conditions for the diagnosis of irritable bowel syndrome (IBS) are inadequate.
- 3) Previous laxative use failed to provide satisfactory relief.
- 4) Participants aged 18 to 75 years old.
- 5) Two or fewer CSBMs per week during the 2-week baseline assessment (run-in) period.
- 6) No use of medicine for constipation during the 2 weeks before enrolment (except rescue medication usage); no acupuncture treatment for constipation in the previous 1 month; no participation in any other on-going trial.
- 7) Volunteered to join this trial and signed the informed consent.

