#### 10. Subject Evaluations and Outcomes

#### 10.1 Baseline Evaluations

Outcomes contain the complete spontaneous bowel movements (CSBMs), spontaneous bowel movements (SBMs), stool consistency (according to Bristol Stool Scale), straining during the defecation, rescue medicine used, and the form of Chinese-version Patient Assessment of Constipation Quality of Life (PAC-QOL). Participants will record their bowel movements, constipation-related symptoms, medicine used for constipation every day through week -2, week -1, weeks 1-8, weeks 11-12, weeks 15-16, weeks 19-20, and weeks 31-32. In both groups, participants without bowel movements (BMs) for 3 or more consecutive days were allowed to use bisacodyl (5-10mg a day before bedtime, Boehringer Ingelheim) or 110 ml glycerol enema as rescue medicine with documentation (time, dosage, and frequency of use) in the stool diary.

The SBMs are the bowel movements that occur in the absence of rescue medicine, or other assistant methods (laxatives, enemas, suppositories usage, or digging out by fingers) within the preceding 24 hours, which include the CSBMs. When participants used rescue medicine, or other measures for constipation, the defecation within 24 hours was considered a non-spontaneous bowel movement, whereas defecation exceeding 24 hours was deemed an SBM. CSBMs were the SBMs with the sensation of complete evacuation.

Outcome record time point: Baseline (the last day of week -2 and week -1), week 2, week 4, week 6, week 8, week 12, week 16, week 20, and week 32 (Figure 1).

[figure not shown]
Outcome assessing time frame: baseline period (weeks -2 to week -1), the latter 6-week treatment (weeks 3-8), the first 2-week treatment (weeks 1-2), and the follow-up periods (weeks 11-12, weeks 15-16, weeks 19-20, weeks 31-32).

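### The primary responder analysis adjusts for centre only and leaves out the run-in CSBM rate, which probably costs a few points of power at most; the planned test remains valid

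*Supplement*

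**What the plan says.** SAP 13.5 defines the endpoint: "The primary outcome was the proportion of participants with 3 or more mean weekly CSBMs over weeks 3-8". It then gives the whole of the primary analysis: "The Cochran-Mantel-Haenszel (CMH) test, stratified by center, was used to test a hierarchical comparison between two groups". Final protocol 7.3 agrees: "For the primary outcome, the CMH test will be used to avoid the center effect". Neither document names another adjustment for this endpoint. The only sensitivity analysis named, in SAP 13.3, is the per-protocol set.

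The run-in rate is collected on everyone. SAP 10.1 has participants keep a daily diary in the two weeks before treatment and lists that window among the assessment periods: "Outcome assessing time frame: baseline period (weeks -2 to week -1"). It is needed for eligibility, since SAP 6.1 requires "Two or fewer CSBMs per week during the 2-week baseline assessment (run-in) period". It is also needed for the analysis set: "Modified intention-to-treat (mITT) set will be defined as all the participants who accept randomization with baseline data" (SAP 13.2).

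For the change in mean weekly CSBMs, SAP 13.6(3) specifies a repeated-measures model in which "the baseline CSBMs data and usage of rescue medicine were set as the covariate".

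**The concern.** The endpoint is the week 3–8 diary average cut at 3 per week, and the run-in rate is an earlier reading of the same quantity. Someone entering at 0 CSBMs per week must gain 3 to respond; someone entering at 2 must gain 1. If run-in rate predicts response within centres, a centre-only analysis leaves that predictable variation in the standard error. It also leaves any chance imbalance in run-in rate in the estimate, because randomisation is stratified by centre alone.

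A non-inferiority conclusion depends on how far the lower confidence limit for EA minus prucalopride lies from -10 points, so the standard error matters directly. At the one-sided 0.025 level of SAP 13.3 the trial has no power to spare, as the figures below show.

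**Working it through.** **Inputs.** From SAP section 9 (the same in final protocol 2.4.2): EA 31.67%, prucalopride 30.9%, margin -10 points, one-sided 5%, 80% power, 20% dropout, 560 recruited (280 per arm). From SAP 13.3: primary test at one-sided 0.025. Not in the documents: any correlation between run-in CSBM rate and response, or any distribution of run-in rates.

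**The plan's own figure.**
- V = 0.3167 × 0.6833 + 0.309 × 0.691 = 0.430.
- Distance from the assumed difference to the margin: 0.0077 + 0.10 = 0.1077.
- n = (1.645 + 0.845)² × 0.430 / 0.1077² = 229.8, so 230 per arm, and 230 × 1.2 = 276. Both stated figures reproduce.

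**Power as planned.** Evaluable n = 280 × 0.8 = 224 per arm. SE = √(0.430/224) = 0.0438, and 0.1077/0.0438 = 2.46.
- One-sided 0.05: Φ(2.46 − 1.645) = 79.2%.
- One-sided 0.025: Φ(2.46 − 1.96) = 69.1%.

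**Power with run-in rate added.** Let R² be the share of within-centre responder variance that run-in rate explains. Then SE becomes 0.0438 × √(1 − R²), and power = Φ(0.1077/SE − z).

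| Assumed R² | SE | Interval narrower by | Power, one-sided 0.025 | Power, one-sided 0.05 | n per arm for 80% power at 0.025 |
|---|---|---|---|---|---|
| 0 (as planned) | 0.0438 | – | 69.1% | 79.2% | 291 |
| 0.01 | 0.0436 | 0.5% | 69.5% | 79.6% | 289 |
| 0.05 | 0.0427 | 2.5% | 71.3% | 81.0% | 277 |
| 0.10 | 0.0416 | 5.1% | 73.6% | 82.8% | 262 |
| 0.20 | 0.0392 | 10.6% | 78.5% | 86.5% | 233 |

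At R² = 0.10 the adjustment is worth 224/0.9 = 249 evaluable per arm, about 25 more than planned.

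**Which R² is plausible.** Eligibility restricts the covariate, and a two-week count is a noisy reading of a person's rate. This was simulated with assumed gamma-distributed personal rates (mean 0.5 or 0.8 CSBMs per week), a 14-day Poisson count, entry kept at 2 or fewer per week, and a 31% response rate tied to the personal rate through a latent correlation:

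| Latent correlation | Observed correlation, run-in with response | R² |
|---|---|---|
| 0.2 | 0.10 | 0.01 |
| 0.4 | 0.20 | 0.04 |
| 0.6 | 0.32 | 0.10 |
| 0.8 | 0.43–0.44 | 0.19–0.20 |

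Latent correlations of 0.2 to 0.6 therefore give R² of about 0.01 to 0.10. The gain is 0.4 to 4.5 points of power at one-sided 0.025 and 0.4 to 3.6 points at one-sided 0.05.

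A more favourable assumption, with run-in values in half-steps from 0 to 2 and a latent correlation of 0.5, gave an observed correlation of 0.37 and a variance ratio of 0.86. Power then rose from 69.3% to 75.3% and from 79.5% to 84.2%. The standardised difference averaged 0.0077, equal to the true value.

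**The case against.** A CMH analysis stratified by the only randomisation factor is conventional and valid. Chance imbalance in run-in rate is already covered by its error rate, and leaving out an optional covariate needs no defence. That stands: this is an improvement in efficiency, not the repair of an error.

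The contrast with SAP 13.6(3) is also weaker than it looks. That item models change from baseline, where baseline is linked to the outcome by construction and is routinely included. It does not say that run-in rate predicts response. The responder outcomes in 13.5, 13.6(1) and 13.6(2) are handled alike, so a reader who infers that the SAP contradicts itself goes too far. What 13.6(3) shows is that the covariate is already in the analysis data.

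A reader might also infer a gain of 9 to 12 points, by assuming a correlation of 0.5 between run-in rate and response (R² = 0.25; power 88.4% at one-sided 0.05 and 81.0% at 0.025). The documents do not support that. They give no correlation, and with entry capped at 2 per week even a latent correlation of 0.8 reached R² of only about 0.20.

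Nor should the drop from 79.2% to 69.1% be counted here. It comes from sizing at one-sided 0.05 and testing at one-sided 0.025, a separate matter that costs about 10 points, more than adjustment would recover over the R² values tabulated.

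Finally, precision gains from adjustment are a large-sample property, and only the within-centre association counts. With a weak covariate the gain may be nil.

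**Conclusion.** The point holds as a modest, nearly free gain in efficiency. The decisive analysis omits an earlier measurement of its own endpoint that every mITT participant has. The likely benefit is a few points of power at most, and an interval about 0.5% to 5% narrower.

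This rests on the plan's response rates, on 224 evaluable per arm, and on an assumed within-centre R² of 0.01 to 0.10. Larger gains need a stronger association than the capped entry range makes likely. A reader might take the omission to mean that the planned estimate is biased or that type I error is inflated; nothing in the documents supports either reading.

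**What to change.** Before unblinding, amend SAP 13.5 and protocol 7.3 as follows.

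- **Primary estimate:** fit a logistic model with treatment, centre and run-in mean weekly CSBMs. Average the predicted risks over all participants under each arm, and take the difference. Compare its lower confidence limit, from a robust or bootstrap variance, with -10 points. This is a marginal risk difference, so the margin keeps its meaning; a conditional odds ratio could not be set against it.
- **Missing data:** fit the model within each multiply imputed dataset (SAP 13.3) and combine the results.
- **Covariates:** do not carry over rescue use from 13.6(3). When taken on treatment it is measured after randomisation.
- **Supportive analysis:** keep the centre-stratified Mantel-Haenszel risk difference.

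The cost is SAP and protocol wording plus a little code, with no new data. The small downside is an estimate standardised through a model rather than a simple stratified difference. Protocol 6.8 has the SAP approved before database lock, but the documents do not show whether unblinding has already taken place. If it has, the adjusted estimate belongs among the supportive analyses.

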# 2.3 Study Objective and Hypothesis

The objective of this trial is to evaluate if the effect of EA is non-inferior to prucalopride for SCC. In addition, we also would like to evaluate whether the therapeutic efficacy of EA could sustain for 3 months or 6 months? The safety and acceptance of EA will be simultaneously evaluated.

Hypothesis: EA is non-inferior to prucalopride for severe chronic constipation over weeks 3-8.

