#### 13. Statistical Analysis

### 13.1 Objective and Hypothesis

#### Objective

Through comparing the efficacy of EA and prucalopride, we aim to evaluate if the effect of EA will be non-inferior to that of prucalopride. We also will evaluate if the therapeutic effect of EA could sustain for 3~6 months.

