#### **Hypothesis**

The primary outcome is the proportion of participants with 3 or more mean weekly CSBMs. The non-inferior margin of the primary outcome is set as -10%.

H0: AEA-BPrucalopride <-10%; H1: AEA-BPrucalopride >-10%.

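### The only test named for the primary outcome, a CMH test, is not linked to the -10 point non-inferiority null and as written could support non-inferiority only by showing superiority

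*Supplement*

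**What the plan says.** The hypothesis is clear. Protocol 2.3 states: "Hypothesis: EA is non-inferior to prucalopride for severe chronic constipation over weeks 3-8". SAP 13.1 adds "The non-inferior margin of the primary outcome is set as -10" per cent and writes the hypotheses for the difference EA minus prucalopride against that value, as does protocol 7.1. The sample size sections (protocol 2.4.2, SAP 9) put the same margin into the formula.

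The analysis sections do not carry the margin forward. Protocol 7.3: "For the primary outcome, the CMH test will be used to avoid the center effect". SAP 13.5: "The Cochran-Mantel-Haenszel (CMH) test, stratified by center, was used to test a hierarchical comparison between two groups". SAP 13.3 fixes sidedness and level ("The primary outcome was one-tailed test at significance levels of 0.025") and requires multiple imputation of the primary outcome in the mITT set, without saying how results are combined. Protocol 7.3 and the sample size sections use a one-sided level of 0.05 instead (SAP 9: "one-sided 5% level of significance, a power of 80% and allowing for a 20% dropout").

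No section names a risk difference, a confidence interval for it, a margin-shifted statistic or a rule comparing a limit with -10 points. The 95% interval in protocol 7.3 is a summary format for continuous data; categorical data get percentages.

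**The concern.** A non-inferiority claim needs a statistic that measures distance from the margin. The CMH statistic measures distance from zero difference (common odds ratio 1). It yields neither an estimate on the scale of the margin nor a limit to hold against it.

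Nothing in SAP 13.5 signals a non-inferiority variant. SAP 13.6 describes secondary responder outcomes, which have no margin, in nearly identical terms: "For the proportion of participants with 3 or more mean weekly CSBMs, the Cochran-Mantel-Haenszel (CMH) test, stratified by center".

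At stake is the trial's one confirmatory decision. Either the literal test is applied, and the trial has almost no chance of success at its own planning rates, or the estimator, centre weights, variance and decision rule are chosen outside the plan. A further, lesser difficulty is that a CMH chi-square does not combine directly by Rubin's rules, so the imputation required by SAP 13.3 has no defined end point.

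**Working it through.** **Inputs.** EA rate 0.3167, prucalopride rate 0.309, margin 0.10, recruitment 560 (280 per arm), dropout 20% (all SAP 9 and protocol 2.4.2), so 280 × 0.8 = 224 per arm. One-sided level: 0.025 (SAP 13.3) or 0.05 (protocol 7.3, SAP 9).

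**1. The plan's own figure.** Variance sum: 0.3167 × 0.6833 + 0.309 × 0.691 = 0.4299. Then n = (1.645 + 0.845)² × 0.4299 / (0.0077 + 0.10)² = 229.8, rounded up to 230. The stated 230 reproduces, so the trial is sized for a test against -10 points.

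**2. Chance that each test succeeds at the planning rates.** SE = √(0.4299/n), which is 0.0438 at 224 and 0.0392 at 280 per arm.

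- Zero-difference test favouring EA: Φ(0.0077/SE − z).
- Test against the margin: Φ(0.1077/SE − z).

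| Per arm | One-sided level | Zero-difference test | Margin test |
|---|---|---|---|
| 224 | 0.025 | Φ(0.176 − 1.960) = 3.7% | Φ(2.458 − 1.960) = 69.1% |
| 280 | 0.025 | Φ(0.197 − 1.960) = 3.9% | Φ(2.749 − 1.960) = 78.5% |
| 224 | 0.05 | 7.1% | 79.2% |
| 280 | 0.05 | 7.4% | 86.5% |

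**3. If a non-significant CMH result were read as non-inferiority.** This is conditional: the plan does not say it. Put EA exactly at the margin, 0.209 against 0.309. Variance sum: 0.209 × 0.791 + 0.309 × 0.691 = 0.3788. The chance of a non-significant two-sided 5% result is Φ(1.96 − 0.10/SE), the other tail being negligible.

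- 224 per arm: SE = 0.0411, Φ(1.96 − 2.432) = 31.9%.
- 280 per arm: SE = 0.0368, Φ(1.96 − 2.719) = 22.4%.

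The nominal error is 2.5%, and the excess grows as evaluable numbers fall.

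**4. Check by simulation.** 40,000 trials per setting, 14 equal centres, 16 or 20 per arm per centre, the same response rates in every centre, CMH without continuity correction. The margin test used a centre-stratified risk difference with a within-centre binomial variance (not Sato's). At one-sided 0.025 and the planning rates, CMH favoured EA in 3.6% (224) and 4.0% (280), and the margin test succeeded in 69.1% and 78.6%. At a true difference of -10 points, CMH was non-significant in 32.2% and 22.3%, while the margin test rejected in 2.5% and 2.4%.

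**The case against.** The strongest reply is that the plan never states a zero-difference null for its primary outcome. It writes the hypotheses against -10 points, sizes the trial on them and makes only the primary analysis one-tailed. Protocol 7.3 introduces CMH as the way to deal with centre effects. Read together, this could mean a one-tailed, centre-stratified test of the stated null with its details left out. That is fair as far as it goes: what the text shows is a missing link between margin and statistic, not a deliberate choice of the wrong null. But the named test has a standard meaning, and the same description serves outcomes without a margin, so the missing details cannot be recovered from the documents.

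Three stronger inferences should be resisted.

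- A reader might conclude that the analysis cannot answer the question at all. A CMH result significantly favouring EA would show superiority and therefore imply non-inferiority. It is merely rare at the planning rates.
- A reader might conclude that the plan will treat non-significance as non-inferiority. No section says so. The 22% to 32% error describes a possible misuse, not the plan's rule.
- A reader might extend the -10 point margin to the follow-up windows, because SAP 13.1 also says "We also will evaluate if the therapeutic effect of EA could sustain for 3~6 months". The margin is set for the primary outcome and the hypothesis for weeks 3-8. SAP 13.3 makes all other analyses two-tailed, and no follow-up non-inferiority hypothesis is stated. Whether an effect persists does not by itself require non-inferiority to prucalopride, and comparisons with baseline and the repeated-measures models through weeks 31-32 also bear on it. Imposing the margin there would add claims that the plan does not make, with no multiplicity rule.

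**Conclusion.** The point stands for the primary analysis and should be fixed before the analysis is run. The design is a margin test with about 69% to 79% power at one-sided 0.025 (79% to 86.5% at 0.05). The analysis as named reaches a conclusion only through superiority, in about 4% of trials at 0.025 (about 7% at 0.05).

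The figures assume the planning rates are true and use a normal approximation; the simulation adds equal centres with common response rates. The range from 224 to 280 per arm reflects that multiple imputation recovers some but not all of the information lost to dropout, so the effective size lies between the two. Real variation between centres would move the figures somewhat but would not put a margin into the CMH statistic. The pooling difficulty is secondary and disappears with the same fix.

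**What to change.** In SAP 13.5 and protocol 7.3, for weeks 3-8 only:

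- Make the primary analysis the centre-stratified Mantel-Haenszel risk difference, EA minus prucalopride, with a Sato-type variance.
- Compute both in each imputed data set and combine estimate and variance by Rubin's rules. This is why an estimate with a variance is preferable here: a score interval such as Miettinen-Nurminen does not pool directly in that way.
- Declare non-inferiority if the lower limit of the two-sided 95% confidence interval lies above -10 percentage points.
- Keep the CMH test only as a superiority test after non-inferiority has been shown.

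The 95% interval matches the one-sided 0.025 in SAP 13.3. Protocol 7.3 and the sample size sections say 0.05, so the two must be reconciled. If 0.025 is kept, the plan's formula gives (1.960 + 0.842)² × 0.4299 / 0.1077², or 291 per group before dropout, and the sample size section should state the power that follows.

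The cost is a few sentences in two documents and a few lines of code. No new data or participants are needed.
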